#### PROC FREQ;

TABLES group\*cured / RISKDIFFC;

WEIGHT counts;

RUN;

The analyses specified above (the proportion of subjects with sero-reduction or seroconversion and an asymptotic 95% CI for the 60-day nifurtimox regimen, and the difference of two independent proportions for the 60-day and 30-day regimens and an asymptotic 95% CI) will also be done using data from Days 7 (Visit 3), Days 30 (Visit 6), the EOT visit (Visit 8), and Days 240 (Visit 10). In the event of small sample sizes for the subgroups, an exact 95% CI will be calculated instead of an asymptotic one.

#### Sensitivity analyses of the primary efficacy variable

The following sensitivity analyses for the primary efficacy variable will be performed:

- Missing values due to the following reasons treated as treatment failures and other missing values excluded from analysis:
  - 1. the reason for discontinuation is known or suspected to be treatment ineffectiveness or an AE,
  - 2. a subject has not had a negative serology at any visit and has no serology determination for the primary analysis visit,
  - 3. an indeterminate or incorrectly performed serology determination occurs at the primary analysis visit (e.g. missing values due to lab procedure, not enough sample materials to perform the test, performance error, etc.).
- Observed data only
- Analysis on PPS

## Subgroup analyses of the primary efficacy variable

The proportion of nifurtimox subjects with sero-reduction or sero-conversion (60-day regimen) and an asymptotic 2-sided 95% CI for the proportion will be calculated by country and for each age stratum.

The same proportion and an asymptotic 2-sided 95% CI for the difference of the 60-day and 30-day nifurtimox regimens will also be summarized by country and for each age stratum.

BAY No. A2502/IMPACT No. 16027

Page:

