Since 1991, the estimated global prevalence of *T. cruzi* infection has decreased from 18 million to 8 million due to intensive vector control and blood bank screening. The PAHO estimates that approximately 60,000 new *T. cruzi* infections occur each year [1]. As other transmission routes have diminished, the proportion of infections attributable to congenital infection has increased. An estimated 26% of incident infections now occur through mother-to-child transmission. Mortality among infected infants is significantly higher than in uninfected infants, ranging from less than 5% to 20% in published studies [7][8]. However, even severe congenital Chagas' disease may not be recognized because signs are often nonspecific, or because the diagnosis is not considered. Children younger than 2 years of age appear to be at higher risk of severe manifestations than older individuals. Severe acute Chagas' disease carries a substantial risk of mortality [8].

In *T. cruzi* infection, treatment with nifurtimox reduces the severity of symptoms, and shortens the clinical course and duration of detectable parasitemia. Parasitological cure is reported in 60% to 85% of patients treated in the early phase. Furthermore, published evidence suggests that if the duration of infection is less than 1 year, the percentage of patients cured (i.e., elimination of parasites) approaches 100% [5][6].

Nifurtimox is well tolerated in children, but its pharmacology in the pediatric population is still not well defined. The currently available marketed product was developed for adults, and there is a significant need for a pediatric formulation particularly for infants and newborns to support weight-adjusted dosing.³³ The safety profile of the drug is relatively well-

³² Text modified for clarity (Amendment 1)

³³ Text modified for clarity, and per changes as a result of Amendment 1

	Integrated Clinical Study Proto	ocol
	BAY A2502 / 16027	
03 NOV 2020	Version 11.0	Page: 24 of 259

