Alternative and more rapid approaches as an early indicator of negative sero-conversion in treated patients have been suggested. Using non-conventional serological techniques, i.e., highly sensitive and specific chemiluminescent ELISA using a purified trypomastigote glycoconjugate antigen and an epimastigote complex [20], the time to negativization was significantly sooner for the non-conventional ELISA than for the conventional ELISA. The chemiluminescent ELISAs provide tests that are highly sensitive and specific for Chagas' disease diagnosis. They can be used in blood bank screening and to monitor the treatment of patients undergoing chemotherapy [21].⁷⁶

Non-conventional ELISA antigens, such as those used in the Sosa-Estani and deAndrade trials (i.e., F29 and F 2/3), [15][16] are often considered as early markers for effective Chagas' disease therapy. In the study by Altcheh, et al, the kinetics of disappearance of conventional serology and anti-F2/3 antibodies were compared in 21 patients with congenital Chagas' disease after receiving benznidazole treatment. Patients were divided into two groups: (A) age < 8 months at diagnosis and (B) age > 9 months at diagnosis. Group A presented negative outcome for conventional serology at 6.6 months (CI 95 3.4-9.8 months) and for anti-F2/3 at 4 months (CI 95 0.9-7.1 months, p = 0.18). Group B exhibited nonreactive conventional serology at 63.1 months (CI 95 42.1-84.2 months) whereas anti-F2/3 antibody determination became negative at 21.9 months (CI 95 5.7-38.1 months, p = 0.0025). In patients belonging to Group A, antibodies were undetectable by both conventional serology and anti-F2/3 ELISA soon after receiving chemotherapy. In infants included in Group B, a negative result for anti-F2/3 antibody detection occurred significantly in advance of negative conventional serology reactivity. Consequently, the anti-F2/3 antibody assay becoming negative should be considered as a surrogate endpoint for assessment of cure or positive response to treatment, particularly in those patients with prolonged time of infection [18].

A new perspective on Chagas' disease diagnosis was opened by the use of the PCR as a measure of treatment response. Over the past few years, the availability of PCR to detect *T. cruzi* DNA in blood samples has opened new possibilities for the evaluation of response to trypanocidal chemotherapy.⁷⁷

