## 4. General Statistical Considerations

## 4.1 General Principles

The statistical evaluation will be performed using the software package SAS release 9.2 or higher (SAS Institute Inc., Cary, NC, USA). Unless otherwise specified, all significance tests will be conducted using a 2-sided alpha level of 0.05, and confidence intervals (CIs) will be 2-sided 95% intervals. All variables collected in this study will be summarized with descriptive statistics at each assessment time. For continuous variables, descriptive statistics will include the number of data available and missing data, means, standard deviations, medians, minimums, and maximums. For categorical variables, frequency counts and percentages will be provided. These will be calculated for each age stratum by treatment regimen, as well as the overall set of study subjects.

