#### Primary analysis of the primary efficacy variable

The difference in the proportion of nifurtimox subjects with sero-reduction or sero-conversion (60-day regimen) and the proportion estimated from historical data will be tested using an asymptotic 2-sided 95% CI with a continuity correction of 1/2n for a single proportion.

The null hypothesis  $H_0$  is  $p_{nifurtimox} = p_{placebo}$ 

The alternative hypothesis H1 is  $p_{nifurtimox} \neq p_{placebo}$ , where pt is the cure rate for treatment t.

Superiority will be confirmed if the lower limit of the CI for the proportion of nifurtimox subjects (60-day regimen) with sero-reduction or sero-conversion is greater than 16%. The proportion and asymptotic 2-sided limits ( $p_l$ ,  $p_u$ ) of the 95% CI for  $p_{nifurtimox}$  can be computed by [3]

$$\hat{p}_{nifurtimox} = x/n$$

$$p_u = \hat{p}_{nifurtimos} + 1.96 \sqrt{\hat{p}_{nifurtimos}(1 - \hat{p}_{nifurtimos})/n} + 1/2n$$

$$p_l = \hat{p}_{nifurtimox} - 1.96 \sqrt{\hat{p}_{nifurtimox}(1 - \hat{p}_{nifurtimox})/n} - 1/2n$$

where x denotes the number of nifurtimox subjects with sero-reduction or sero-conversion and n the total number of subjects in 60-day regimen group. The SAS code will be:

PROC FREQ;

TABLES cured / BINOMIALC;

WEIGHT counts;

RUN;

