#### Secondary analysis of the primary efficacy variable

A secondary analysis will be done to compare the proportion of subjects with sero-reduction or sero-conversion for the 60-day and 30-day nifurtimox regimens. This will be performed using an asymptotic 2-sided 95% CI for the difference of two independent proportions.

The null hypothesis  $H_0$  is  $p_{nifurtimox, 60d} = p_{nifurtimox, 30d}$ 

The alternative hypothesis H1 is  $p_{nifurtimox, 60d} \neq p_{nifurtimox, 30d}$ , where  $p_t$  is the cure rate for treatment *t*.

Difference in efficacy between the two groups will be confirmed if the CI for the difference of two proportions of nifurtimox subjects (60-day regimen *versus* 30-day regimen) with sero-reduction or sero-conversion does not include 0. The proportions and asymptotic 2-sided limits ( $l_l$ ,  $l_u$ ) of the 95% CI for *pnifurtimox*, 60d - *pnifurtimox*, 30d can be obtained by [3]

$$\begin{split} \hat{p}_{i} &= \frac{x_{i}}{n_{i}}, \qquad i = 1, 2. \\ l_{u} &= (\hat{p}_{1} - \hat{p}_{2}) + 1.96\sqrt{(\hat{p}_{1}(1 - \hat{p}_{1})/n_{1}) + (\hat{p}_{2}(1 - \hat{p}_{2})/n_{2})} + \frac{1}{2} \left(\frac{1}{n_{1}} + \frac{1}{n_{2}}\right) \\ l_{l} &= (\hat{p}_{1} - \hat{p}_{2}) - 1.96\sqrt{(\hat{p}_{1}(1 - \hat{p}_{1})/n_{1}) + (\hat{p}_{2}(1 - \hat{p}_{2})/n_{2})} - \frac{1}{2} \left(\frac{1}{n_{1}} + \frac{1}{n_{2}}\right) \end{split}$$

where  $p_i$ ,  $x_i$  and  $n_i$  denote the cure rate, the number of nifurtimox subjects with sero-reduction or sero-conversion, and the total number of subjects, for treatment *i* respectively. Treatment *i*=1, 2 represents 60-day and 30-day nifurtimox regimens, respectively.

The SAS code will be:

*Reference Number: BPD-SOP-060 Supplement Version: 6* 

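### Early-visit, country and age-stratum cure rates default to asymptotic intervals that fail near 0% and 100%, and the exact-interval fallback covers only part of the gap

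*SAP*

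**What the plan says.** All of this is in SAP 6.2.1.1 unless noted.

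- **Primary proportion.** The 60-day cure rate gets an "asymptotic 2-sided 95% CI with a continuity correction of 1/2n for a single proportion", with the formula written out.
- **60- versus 30-day difference.** "This will be performed using an asymptotic 2-sided 95% CI for the difference of two independent proportions". The formula that follows adds a correction of ½(1/n₁ + 1/n₂).
- **Other visits.** Both analyses "will also be done using data from Days 7 (Visit 3), Days 30 (Visit 6), the EOT visit (Visit 8), and Days 240 (Visit 10"). The fallback comes straight after: "In the event of small sample sizes for the subgroups, an exact 95% CI will be calculated instead of an asymptotic one". No sample size or event count defines small.
- **Subgroups.** A later paragraph states that "an asymptotic 2-sided 95% CI for the proportion will be calculated by country and for each age stratum", and treats the regimen difference in the same way. It repeats neither the continuity correction nor the fallback.

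SAP 3.1 targets, but does not require, 38 subjects per age stratum. At 2:1 allocation that is about 25 and 13.

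**The concern.** A Wald-type interval takes its width from the observed p(1-p). At 0% or 100% that term is zero, so only the continuity correction is left, or nothing at all if the correction is not applied. The reported error bar is then smallest where the data say least about the remaining uncertainty.

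The protocol gives some reason to expect such rates. Its benefit-risk assessment says that with infection under one year "the percentage of patients cured (i.e., elimination of parasites) approaches 100" per cent. Its design justification cites a benznidazole study of congenital infection in which, among children under 8 months at diagnosis, "Group A presented negative outcome for conventional serology at 6.6 months", well before the 12-month endpoint. Children older than 9 months at diagnosis in that study took 63.1 months. A low cure rate at Day 7 or Day 30 is therefore a reasonable inference in older children.

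At stake is how the tables read: limits above 100% or below 0%, and infant-stratum estimates that look much more certain than 25 or 38 children allow.

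**Working it through.** **Inputs.** Two-sided 95% intervals (SAP 4.1: "all significance tests will be conducted using a 2-sided alpha level of 0.05"); the SAP 6.2.1.1 formulas; n = 200 and 100 (protocol 10.4); 25 and 13 per stratum (38 split 2:1). The subgroup paragraph does not restate the 1/(2n) correction. I apply it throughout, which favours the plan: without it, 25/25 has zero width.

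**The plan's own figures first.**

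- Half-width of the regimen difference at 55%, 200 versus 100: 1.96·√(0.55·0.45/200 + 0.55·0.45/100) = 0.119, as the protocol states (0.12). With the correction, + ½(1/200 + 1/100) = 0.127.
- Primary rule: the corrected lower limit first exceeds 16% at 44/200. Power at 55% is above 99.99% (stated 99%), and one-sided error at 16% is 1.6%.
- Historical placebo intervals: Clopper-Pearson gives 1.0-12.9% for 3/65 and 0.6-15.5% for 2/44, in line with the tabulated 1-13% and 1-16%. The SAP's own formula would give -1.3 to 10.5% and -2.7 to 11.8%. The controls therefore appear to carry exact intervals already.

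**Single proportions.** Planned: p ± 1.96·√(p(1-p)/n) ± 1/(2n). Exact: Clopper-Pearson, whose lower limit for n/n is 0.025^(1/n) and whose upper limit for 0/n is 1 - 0.025^(1/n).

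| Observed | Planned form | Exact |
|---|---|---|
| 25/25 | 98.0 to 102.0% | 86.3 to 100% |
| 24/25 | 86.3 to 105.7% | 79.6 to 99.9% |
| 13/13 | 96.2 to 103.8% | 75.3 to 100% |
| 0/200 | -0.25 to 0.25% | 0 to 1.83% |
| 2/200 | -0.63 to 2.63% | 0.12 to 3.57% |

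**Difference, 25/25 versus 13/13.** Planned: 0 ± ½(1/25 + 1/13) = ±5.8 points. Newcombe: the Wilson lower limits are 86.7% and 77.2%, so the interval runs from -(100 - 86.7) = -13.3 to +(100 - 77.2) = +22.8 points.

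**Exact coverage of the nominal 95% interval.**

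| n | True rate | Planned form | Clopper-Pearson |
|---|---|---|---|
| 25 | 0.85 | 90% | 98% |
| 25 | 0.95 | 72% | 99% |
| 25 | 0.97 | 53% | 99% |
| 200 | 0.005 | 63% | 98% |
| 200 | 0.01 | 87% | 98% |
| 200 | 0.02 | 91% | 96% |
| 200 | 0.55 | 95% | 96% |

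Coverage near the boundary is erratic, not uniformly low. At n = 25 and a true rate of exactly 0.98 it is close to 100%, because the 25/25 interval happens to start there.

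For differences (25 versus 13) the planned form covers 84% at 0.98 versus 0.90 and 88% at 0.95 versus 0.85, but 99.9% at 0.95 versus 0.95 and 96% at 0.85 versus 0.75. Newcombe covers 96-99% in these four cases.

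**The case against.** **The SAP already has a fallback.** The only subgroups defined in 6.2.1.1 are countries and age strata, so the exact-interval sentence most naturally covers them. If it were applied to every stratum, the single-proportion stratum intervals would be sound. This stands, and a reader should not infer that 25-subject strata must receive Wald intervals. It leaves open the undefined threshold, a trigger that ignores extreme rates, the full arm at early visits, the silence of the subgroup paragraph, and the unnamed method for differences.

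**Boundary rates are not stated for the trial endpoint.** The near-100% figure is parasite elimination, and the preceding sentence gives 60-85% for parasitological cure in early-phase treatment. Below 8 months, cure requires both ELISAs to be negative, and a missing test counts as no cure. The 6.6-month figure comes from a 21-patient study of another drug. No document gives a cure rate for Days 7 to 60, and from 8 months of age a 20% fall in OD counts as cure. At 60-85% with n = 25, the planned interval covers 90-97%. All of this stands: boundary rates are plausible, not established.

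**Nothing is decided on these intervals.** The Part 1 rules for cure rates use whole arms at 12 months: the 16% goal, whether the 60- versus 30-day interval excludes 0, and the 45% benznidazole reference. Subgroup results are only calculated and summarized. A reader might infer that a ±5.8-point infant interval would establish that 30 days matches 60. The SAP does not support that, because it sets no comparability margin for any group.

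**Conclusion.** The concern holds as a defect in descriptive precision. The default interval for early visits, countries and age strata is unreliable near 0% and 100%, and the fallback closes only part of the gap. At the boundary, the distance from the estimate to its limit is understated about sevenfold: 2.0 against 13.7 points at 25/25, and 0.25 against 1.83 points at 0/200. Away from the boundary the interval is adequate.

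The size rests on three assumptions: that rates in some infant strata or early visits do come close to 0% or 100%; that strata reach about 25 and 13 subjects per regimen; and that the 1/(2n) correction carries over to the subgroup intervals.

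A reader might also infer that the primary result is at risk. It is not: at the planned 55% with n = 200, coverage is about 95%, and the 44/200 cut-off holds one-sided error to 1.6%. Severity is minor to moderate.

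**What to change.** In SAP 6.2.1.1, for every country, age-stratum and early-visit analysis (Days 7, 30, EOT and 240):

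- use Clopper-Pearson (or Wilson) 95% intervals for single proportions;
- use Newcombe or Miettinen-Nurminen 95% intervals for the 60- versus 30-day difference;
- delete the switch that depends on small sample sizes, and name the chosen methods in the subgroup paragraph itself.

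Leave the 12-month whole-arm primary interval and its 16% rule as pre-specified. Moving it to an exact interval would lower the cut-off from 44 to 43 of 200 and raise one-sided error from 1.6% to 2.5%, which a problem in descriptive tables does not justify.

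The cost is a few lines of SAP text and changed PROC FREQ options. The downside is somewhat wider, slightly conservative intervals (Clopper-Pearson more so than Wilson).

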## 6.2.1.2 Secondary efficacy variables and analysis

Secondary efficacy variables include clinical signs/symptoms of Chagas' disease (see Appendix 9.1), concentration test for *T. cruzi* (for subjects < 8 months of age ), non-conventional serologic testing, and disease state determined by qPCR ("cure" defined as Not Detectable / "no cure" defined as Detectable).

All secondary efficacy variables, except signs/symptoms of Chagas' disease, will be summarized overall and by treatment regimen at each assessment time for each age stratum.

Signs/Symptoms of Chagas' disease will be summarized for each item (see Appendix 9.1).

The relationship of conventional serology results to qPCR results will be done using frequencies of matches and mismatches on the determination of disease status, and phicorrelation and kappa coefficient to assess the degree of agreement. The relationship of nonconventional serology to conventional serology will be analyzed in the same way. The following SAS code will be used:

PROC FREQ;

TABLES group\*cured / CHISQ AGREE;

WEIGHT counts;

RUN;

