4.1 Objectives for part 1 (CHICO)

The primary objective of this Phase 3 clinical study is:

• To assess the superiority of a 60-day regimen of nifurtimox to historical untreated control at the 12-month follow-up (360 days from end of treatment [EOT]) as sero-reduction (defined as a ≥ 20% reduction in optical density [OD] measured by conventional enzyme-linked immune sorbent assay [ELISA]) compared to baseline in subjects ≥8 months to <18 years of age at randomization; or sero-conversion (defined as negative Immunoglobulin G [IgG] concentration) in all subjects³⁴

Secondary objectives of the study are:

³⁴ Text modified as per amendment 2

	Integrated Clinical Study Protocol	
	BAY A2502 / 16027	
03 NOV 2020	Version 11.0	Page: 25 of 259

- To assess the comparability of a 30-day regimen of nifurtimox to a 60-day regimen of nifurtimox as sero-reduction or sero-conversion at the 12-month follow-up (360 days from EOT)³⁵
- To evaluate the safety/tolerability profile of nifurtimox by laboratory parameters (hematology, blood chemistry, urinalysis), electrocardiogram (ECG) monitoring, vital sign measurements (blood pressure, heart rate, respiratory rate, temperature), adverse event (AE) monitoring, and physical examinations, including neurological examinations³⁶
- To evaluate the pharmacokinetics (PK)/pharmacodynamics (PD) of nifurtimox in children receiving the drug for treatment of Chagas' disease (to be described in a separate report)

Exploratory objectives of the study are:³⁷

- To assess the comparability of a 60-day regimen of nifurtimox to historical active control (benznidazole)³⁸ as sero-reduction or sero-conversion at the 12-month follow-up (360 days from EOT)³⁹
- To assess the comparability of a 30-day regimen of nifurtimox to a 60-day regimen of nifurtimox using quantitative polymerase chain reaction (qPCR) at the 12-month follow-up (360 days from EOT)⁴⁰
- To evaluate the relationship of conventional serology (as sero-reduction or sero-conversion) to qPCR using frequencies of matches and mismatches to assess agreement⁴¹
- To evaluate the relationship of non-conventional serology to conventional serology⁴²
- To evaluate the relationship of conventional serology to IHA^{43,44}

4.2 **Objectives for part 2 (CHICO SECURE)**

The primary objective of the LTFU part of the study is:

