6.1 Inclusion criteria

Inclusion criteria for part 1 (CHICO)

- 1. Male and female pediatric subjects aged 0 days to younger than 18 years
- 2. Chagas' disease diagnosed/confirmed by:
 - Subjects < 8 months of age at randomization must demonstrate direct observation of *T. cruzi* by concentration test⁸⁶
 - Subjects ≥ 8 months to < 18 years of age at randomization must demonstrate a positive conventional ELISA result for both of the following tests to confirm diagnosis:
 - Recombinant ELISA
 - Total purified antigen ELISA⁸⁷

Additionally, a non-conventional ELISA test and IHA ^{88,89} will be obtained; however, a positive result will not be required for diagnosis.

Subjects will also be eligible if there is acceptable documentation (two ELISA tests) of positive Chagas' disease within three months prior to screening and they have not had prior anti-trypanocidal or anti-parasitic treatment.⁹⁰ (The subject's parent or legally acceptable representative must agree to the collection of a baseline blood specimen for ELISA testing later during the study).⁹¹

- 3. Written informed consent by the subject and/or parent(s) or legally authorized representative(s) according to the age established per local regulations must be obtained from all subjects who are screened for the study. In addition, depending on the subject's age, subject's assent is required as applicable by local laws and regulations (varies in each country).
- 4. Females of childbearing potential (i.e., female subjects who have experienced menarche) and male subjects must agree to use adequate contraception if sexually active from the time of signing the informed consent/assent form until 3 months after the last study drug

⁸⁶ Text modified for clarity (Amendment 1)

⁸⁷ Text modified/added for clarity and per Modification 2 (Amendment 1)

⁸⁸ IFA test added per Amendment 5

 $^{^{89}}$ Replaced IFA with IHA per Amendment 6.

⁹⁰ Text added per Modification 2 (Amendment 1)

⁹¹ Text added as per amendment 2.

	Integrated Clinical Study Protocol	
	BAY A2502 / 16027	
03 NOV 2020	Version 11.0	Page: 37 of 259

administration. Depending on the country, study site personnel may dispense condoms at the time that study drug is dispensed to either the subject or the subject's parent/legal guardian, with an explanation of rationale and risks.

Inclusion criteria for part 2 (CHICO SECURE)

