03 NOV 2020

Version 11.0

Page: 254 of 259

Reagents	Final concentration	Volume (x 1 reaction)	Volume (x N reactions)
Roche Fast Start Universal Probe Master Mix (Rox) (2X)	1X	10 µL	N x 10
cruzi 1 (Fw) (50 µM)	0,75 μM	0,3 μL	N x 0,3
cruzi 2 (Rv) (50 µM)	0,75 μM	0,3 μL	N x 0,3
cruzi 3 (probe) (5 µM)	0,05 μM	0,2 μL	N x 0,2
IAC Tq Fw (5 µM)	0,1 µM	0,4 μL	N x 0,4
IAC Tq Rv (5 µM)	0,1 µM	0,4 μL	N x 0,4
IAC probe (5 µM)	0,05 μM	0,2 μL	N x 0,2
H ₂ O PCR quality	-	3,2 μL	N x 3,2
Total volume (mix) x well	-	15 μL	15 μL
DNA sample volume		5 μL	5 μL
Final volume		20 µL	20 µL

- Distribute 15 μ L of the reaction mixture per well.
- Add 5 μ L of DNA sample or controls in the wells following the reaction protocol.
- Seal the plate with the adhesive film without touch the surface.
- Confirm that the samples have been applied in the reaction mixture and not in the edges of the tube.
- Start the reaction

4. Cycles and reaction conditions

First step: 10 min at 95°C.

Second step: 40 cycles of 15 sec at 95°C and 1 min at 58°C, fluorescence data collection in the yellow (IAC-VIC) and green (*T. cruzi*-FAM) channel.

5. Interpretation of results

Establish the threshold in 0.02 to *T. cruzi* and 0.01 to the internal amplification control (IAC).

Analyze the results of PCR negative and positive controls

Run valid:

- Positive controls are detectable to *T. cruzi* analysis (green channel). The fluorescent curve crosses the threshold leading to a Ct appropriate in relation to the concentration of *T. cruzi* DNA in the respective positive control (assess with control chart).
- White controls are not detectable to *T. cruzi* analysis. The fluorescent curve does not cross the threshold leading to absence of Ct.

	Integrated Clinical Study Protocol		
	BAY A2502/ 16027		
03 NOV 2020	Version 11.0	Page:	255 of 259

Valid sample:

- The internal amplification control (yellow channel) amplified with and efficient signal

Positive sample or detectable to *T. cruzi*:

- The fluorescent curve in the green channel crosses the threshold leading to a Ct value.

Negative sample or not detectable to *T. cruzi*:

- The fluorescent curve does not cross the threshold leading to absence of Ct value.

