#### **Statistical Analysis Plan**

#### BAY No. A2502/IMPACT No. 16027 Page: 5 of 30

reduction (defined as  $a \ge 20\%$  reduction in optical density [OD] measured by conventional enzyme-linked immunosorbent assay [ELISA]) compared to baseline in subjects  $\ge 8$  months to < 18 years of age at randomization or sero-conversion (defined as negative Immunoglobulin G [IgG] concentration) in all subjects

Secondary objectives of the study are:

- To assess the comparability of a 30-day regimen of nifurtimox to a 60-day regimen of nifurtimox as sero-reduction or sero-conversion at the 12-month follow-up (360 days from EOT)
- To evaluate the safety/tolerability profile of nifurtimox by laboratory parameters (hematology, blood chemistry, urinalysis), electrocardiogram (ECG) monitoring, vital sign measurements (blood pressure, heart rate, respiratory rate, temperature), adverse event (AE) monitoring, and physical examinations, including neurological examinations
- To evaluate the pharmacokinetics (PK)/pharmacodynamics (PD) of nifurtimox in children receiving the drug for treatment of Chagas' disease

Exploratory objectives of the study are:

- To assess the comparability of a 60-day regimen of nifurtimox to historical active control (benznidazole) as sero-reduction or sero-conversion at the 12-month follow-up (360 days from EOT)
- To assess the comparability of a 30-day regimen of nifurtimox to a 60-day regimen of nifurtimox using qualitative polymerase chain reaction (qPCR) at the 12-month follow-up (360 days from EOT)
- To evaluate the relationship of conventional serology (as sero-reduction or seroconversion) to qPCR using frequencies of matches and mismatches to assess agreement
- To evaluate the relationship of non-conventional serology to conventional serology
- To evaluate the relationship of conventional serology to indirect haemagglutination assay (IHA)

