## 6.1.2 Demographic and Other Baseline Characteristics

Demographics (sex, ethnicity, race, age at randomization, weight, height/length) and baseline characteristics (i.e., ELISA, IHA and qPCR test results, Chagas' disease signs and symptoms) will be summarized overall and by treatment regimen. The same summary will also be performed for each age stratum.

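### SAP 6.2.1.2 counts any undetectable qPCR as 'cure' without requiring a detectable result before treatment, so children undetectable at Visit 1 enter the qPCR cure rates as cures

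*SAP*

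**What the plan says.** **Definition.** SAP 6.2.1.2 includes "disease state determined by qPCR ('cure' defined as Not Detectable / 'no cure' defined as Detectable". It adds that the secondary variables, other than signs and symptoms, "will be summarized overall and by treatment regimen at each assessment time for each age stratum". The suggested laboratory procedure in Protocol Appendix 16.4 also judges each sample alone; a negative is a sample for which "The fluorescent curve does not cross the threshold leading to absence of Ct value". (Protocol 9.4.1 lets the central laboratory's own procedure prevail.)

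**Entry.** Under Protocol 6.1, subjects under 8 months "of age at randomization must demonstrate direct observation of" *T. cruzi*. Those from 8 months to under 18 years "must demonstrate a positive conventional ELISA result for both of the following tests to confirm diagnosis". Documented positive disease in the three months before screening also qualifies. A detectable qPCR is nowhere required.

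**Baseline result.** Protocol 9.4.1 schedules qPCR at screening. SAP 6.1.2 uses it descriptively, listing "ELISA, IHA and qPCR test results" among the baseline characteristics, overall, by regimen and by age stratum.

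**Comparison affected.** Protocol 4.1 has an exploratory objective comparing the 30-day with the 60-day regimen "using quantitative polymerase chain reaction (qPCR) at the 12-month follow-up (360 days from EOT"). SAP 2.1 repeats it but calls the assay qualitative. Beyond the summaries in 6.2.1.2, the SAP gives no method for this comparison.

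**The concern.** 'Cure' implies a change from infected and detectable to undetectable. The SAP's variable records only the state at the visit. An infected child whose parasitaemia is below the detection limit at Visit 1 already meets the definition before the first dose, and meets it again at 12 months if the result simply persists. Such children carry no information about clearance, yet they sit in the numerator and the denominator of both arms.

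Two things are at stake. The reported qPCR cure rates would overstate clearance. The 30- versus 60-day difference would be pulled towards zero, which matters for an objective framed as comparability of a shorter regimen.

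From 8 months of age, serological cure does need a change: either a fall of at least 20% in optical density, or conversion after two positive ELISAs at entry. The two 'cure' labels therefore do not mean the same thing in those children.

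**Working it through.** **1. The plan's own precision figure.** Protocol 10.4 gives a half-width of about 0.12 for the 60- minus 30-day difference with 200 and 100 subjects. At p=0.50:

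1.96 × √(0.25/200 + 0.25/100) = 0.120.

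The SAP's continuity correction, ½(1/200 + 1/100) = 0.0075, makes it 0.1275. The stated figure reproduces, but it belongs to the serological endpoint. No figure is given for the qPCR comparison.

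**2. Effect of the definition.** Let u be the share Not Detectable at Visit 1 (equal across arms in expectation, by randomisation), c the clearance among those Detectable at Visit 1, and s the share of baseline-undetectable children who are undetectable at the later visit.

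- Observed 'cure' = u·s + (1-u)·c
- Observed difference = u·(s60 - s30) + (1-u)·(c60 - c30)

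If baseline-undetectable children all stay undetectable (s=1), this becomes u + (1-u)·c and (1-u)·(c60 - c30). The cure rate is inflated by u·(1-c), and the difference shrinks by exactly (1-u). With no clearance at all (c=0), apparent 'cure' would still equal u.

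**3. Illustration.** Assumed and not in the documents: u, s=1, c60=90%, c30=75% (difference 15 points). Arms are 200 and 100. Intervals use the SAP's continuity-corrected formula.

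| u | 60-day 'cure' | 30-day 'cure' | Difference, all subjects (95% CI), points | Visit 1-detectable arms | Difference, restricted (95% CI), points |
|---|---|---|---|---|---|
| 10% | 91.0% | 77.5% | 13.5 (3.7 to 23.3) | 180/90 | 15 (4.2 to 25.8) |
| 30% | 93.0% | 82.5% | 10.5 (1.5 to 19.5) | 140/70 | 15 (2.6 to 27.4) |
| 50% | 95.0% | 87.5% | 7.5 (-0.4 to 15.4) | 100/50 | 15 (0.1 to 29.9) |
| 70% | 97.0% | 92.5% | 4.5 (-1.9 to 10.9) | 60/30 | 15 (-4.8 to 34.8) |

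Example, u=50%: 0.5 + 0.5×0.90 = 0.95; 0.5 + 0.5×0.75 = 0.875; difference 0.075.

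Power to detect the difference, all subjects versus restricted, is 87% vs 88%, 77% vs 80%, 63% vs 66% and 44% vs 47% down the rows. Restriction changes what is estimated far more than it changes power.

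**4. Plausible size of u.** Protocol 5.1 cites a detection limit of 0.5 parasites/mL for the best PCR methods, and a median pre-treatment load of 6.2 parasite equivalents/mL in school-aged children. Neither gives u. If that median covers all the patients in the cited study, at least half were well above the limit, so values of u above 50% would fit that population poorly.

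**The case against.** The strongest reply is that nothing is decided on this variable. It is secondary, and the regimen comparison by qPCR is exploratory. SAP 6.2.1.2 plans only summaries, and SAP 6.2.1.3 covers benznidazole and IHA. No qPCR difference, interval, margin or comparability rule is specified. A reader might infer that the 30-day regimen would be falsely declared comparable; the documents do not support that, because there is no such declaration to make. Even the serological 30- versus 60-day analysis asks only whether the interval excludes zero. This stands.

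Existing outputs also disclose part of the problem. Baseline qPCR is tabulated by regimen and age stratum, so u would be visible. This stands too, but the table does not correct the later rates.

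Persistence to Day 420 is assumed, not shown. A reader might infer that every child undetectable at Visit 1 remains so; no section says this, and any who later become detectable lower the inflation. The all-subjects contrast is also a valid randomised difference. It answers another question, so calling 15 points the true difference is a choice of estimand.

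A reader might further infer that phi and kappa against serology are invalid. They are not. Their purpose is same-visit agreement on disease status, and a seropositive, qPCR-undetectable child is a genuine mismatch that the table should show. The contrast between a change measure and a state measure is also incomplete: under 8 months no positive ELISA is needed at entry, so sero-conversion has no baseline condition there either.

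What survives is the label and the denominator. The plan calls 'cure' something that can be present before treatment.

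**Conclusion.** The point holds as a definitional flaw in a descriptive secondary variable. Followed as written, SAP 6.2.1.2 counts a child undetectable at Visit 1 as a qPCR cure, mainly in the strata aged 8 months and over. Cure rates are inflated in both arms as long as baseline-undetectable children are undetectable later more often than the others clear. The exploratory regimen difference shrinks by (1-u) to the extent that those children stay undetectable in both arms.

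The direction follows from the definition; the size cannot be derived. It rests on u, on the two clearance rates and on persistence, none of which the documents give, so the table is illustrative only. The primary serological analysis is unaffected, and the case rests on interpretation rather than power.

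**What to change.** In SAP 6.2.1.2:

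- Define qPCR clearance as Not Detectable at the visit among subjects Detectable at Visit 1, and use it for the 30- versus 60-day qPCR comparison.
- Name the method for that comparison; the SAP's existing interval for a difference of two proportions would serve.
- Show subjects Not Detectable at Visit 1 in a separate row, with the number later Detectable.
- Keep the all-subjects result as supportive, labelled 'not detectable' rather than 'cure'.
- Keep phi and kappa on all subjects, with the Visit 1-detectable subset as a supportive analysis only.

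The Visit 1 sample is already collected, and restricting on a pre-treatment result preserves the randomised comparison. The cost is SAP wording and programming, a smaller denominator with wider intervals, and less favourable qPCR rates.
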